8.1.1.1 Screening Phase (Visit 0)

Patients will provide written informed consent. Medical history, physical examination, laboratory studies, ophthalmological evaluation and CT imaging will be performed to determine baseline disease status and trial eligibility. The medical history, physical examination, potential biopsies, ECG and laboratory studies (including biomarkers) must be performed within 21 days before trial entry (Visit C1-V1). CT imaging must be performed within four weeks before trial entry (Visit C1-V1).

A patient may be rescreened one time only. A rescreening must be approved by the sponsor to ensure that the safety of the patient is not compromised.

8.1.1.2 Treatment Phase (C1 to CX)

Dose Escalation Part

The investigator must have evaluated the patient's eligibility and confirm receipt of sponsor decision and patient number before the patient's first infusion.

Tisotumab vedotin (HuMax-TF-ADC) will be administered on Days 1, 8 and 15 of a 28-day cycle. Dose escalation to MTD is anticipated to involve up to three dose levels with an anticipated maximum dose level of 1.5 mg/kg.

Patients will receive four cycles (each with three doses) of tisotumab vedotin (HuMax-TF-ADC) at 28-day intervals. Thus, the treatment period will last for 16 weeks or until the patient withdraws from the treatment/trial due to the withdrawal criteria.

After four cycles, if there is evidence of the patient benefitting from treatment, at the discretion of the treating physician, there is an option to continue in the trial for up to a maximum of eight additional cycles (32 weeks) or until the patient withdraws from the treatment/trial due to the withdrawal criteria.

The treatment period will have a maximum duration of 48 weeks.

Cohort Expansion Part

The investigator must have evaluated the patient's eligibility before the patient's first infusion.

Tisotumab vedotin (HuMax-TF-ADC) will be administered on Day 1, 8 and 15 of a 28-day cycle. Twenty to 30 patients will receive up to nine cycles of three doses of HuMax-TF-ADC at the dose determined by the sponsor in agreement with the DMC based on the Dose Escalation part of the trial.

Severe ocular toxicity has been observed at 1.2 mg/kg 3q4wk. Patients will no further receive the 3q4wk schedule; instead tisotumab vedotin (HuMax-TF-ADC) 2.0 mg/kg will be administered once q3wk, on Day 1 of each 21-day cycle, regardless of the prior dose(s) administered. The next dose of tisotumab vedotin cannot be administered until at least 21 days have elapsed since the last administration.

Final 5.0 (incorporating Protocol Amendment 4) 06 Jul 2017

The treatment period will last for up to 36 weeks (or less after changing to the once q3wk dosing scheme) or until unacceptable toxicity or disease progression at the discretion of the treating physician.

8.1.1.3 Unscheduled Visit (U1 to UX)

If deemed necessary by the investigator, the patient may be called in for an unscheduled visit(s). During an unscheduled visit the investigator can perform any trial relevant clinical or laboratory assessments deemed necessary. The visit date and reason for visit must be recorded in the patient's medical records and electronic case report form (eCRF).

8.1.1.4 Follow-up Phase

Dose Escalation Part

Patients will attend four follow up visits (FU1 to FU4) at six weekly intervals (± 7 days).

If the patient withdraws from treatment and has not started new anti-cancer treatment, or if the patient completes all treatment cycles, the patient will be followed by the site every six weeks for a maximum of four visits or until other treatment is initiated, for a maximum of 24 weeks. Then, the patient will return for an End of Trial (EOT) Visit.

Cohort Expansion Part

No follow-up visits will be included in the Cohort Expansion part.

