8.3.4.3 Evaluations at Withdrawal from Treatment

When a patient withdraws from treatment, he/she should return for follow-up visits and the End of Treatment page must be filled in.

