12.3 Statistical Methods

The presentations will be done separately for the Dose Escalation part and the Cohort Expansion part.

In the reporting of the Dose Escalation part tables will report by cohort, while in the Cohort Expansion part tables will report by indication.

The shift from the 3q4wk dosing to the once q3wk dosing in the Cohort Expansion part may lead to a need for reporting some tables by dosing schedule. This will be described as appropriate in the SAP.

No formal statistical tests will be performed.

For efficacy analyses, the quartile estimates of PFS and DoR from the Kaplan-Meier product limit algorithm will be presented (Kaplan and Meier, 1958). The 2-sided 95% confidence interval will be presented as well. The number of events may be small, and thereby limit use of the Kaplan-Meier method to provide reliable information. In this case, descriptive statistics (e.g., n, mean, standard deviation, median, minimum and maximum) for PFS or DoR will be presented. Objective response (CR or PR) rate will be determined along with the corresponding 2-sided 95% exact binomial confidence interval.

All data will be listed. Baseline is defined as the latest available measurement made before the first treatment with tisotumab vedotin (HuMax-TF-ADC).

A patient will be considered as having completed the trial when all planned trial visits have been performed.

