control/relief/eliminate endpoints, it is recommended that post-treatment changes are recorded as either "no new lesions" or "new lesions." However, PD at the first scheduled assessment should be confirmed on a second scan performed six or more weeks later, in the absence of clearly worsening soft-tissue (nodal and visceral) disease or disease-related symptoms. In case where visible lesions disappear, this should be confirmed at the next scheduled assessment too.

For patients with ovarian and endometrial cancer, a response according to CA 125 has occurred if there is at least a 50% reduction in CA 125 levels from a pretreatment sample. The response must be confirmed and maintained for at least 28 days. Patients can be evaluated according to CA 125 only if they have a pretreatment sample that is at least two × ULN and within two weeks prior to starting treatment.

Evaluation of best overall response

The best overall response is the best response recorded from the start of the treatment until disease progression/recurrence (taking as reference for PD the smallest measurements recorded since the treatment started).

Patients with a global deterioration of health status requiring discontinuation of treatment without objective evidence of PD at that time should be classified as having "symptomatic deterioration". Every effort should be made to document the objective progression even after discontinuation of treatment.

Confirmation

SD: follow-up measurements must have met the SD criteria at least once and for a minimum time period of six weeks (\pm 7 days) after first treatment.

PR and CR: no formal confirmation response is required. However, a repeat CT-scan will be performed no less than four weeks (± 7 days) after the criteria for response is met to substantiate/confirm CT response (Section 10.7).

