12.5.3.3 Progression-free Survival

Progression-free survival is defined as the number of days from Day 1 in Cycle 1 to first PD or death. Progression-free survival will be derived for all patients and presented graphically as well as summarized using survival analysis methods.

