12.5.3.4 Duration of Response

Duration of response is defined as the number of days from the first documentation of objective tumor response (CR or PR) to the date of first PD or death.

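### Cohort Expansion schedules no tumour assessment after the EOT Visit, although two general instructions call for follow-up after treatment stops, so PFS and DoR lose events and may be informatively censored

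*Protocol*

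**What the plan says.** Three sections of the Protocol deal with what happens after treatment stops.

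- Section 8.1.1.4 rules out post-treatment visits in one part of the trial: "No follow-up visits will be included in the Cohort Expansion part". For Dose Escalation the same section provides six-weekly visits "for a maximum of four visits or until other treatment is initiated, for a maximum of 24 weeks", and Table 1 marks a CT-scan in its follow-up column. Table 5, the current Cohort Expansion flow chart, has no follow-up column.
- Section 8.3.4.3, which names no part, says: "When a patient withdraws from treatment, he/she should return for follow-up visits and the End of Treatment page must be filled in".
- Section 12.5.3.1, also without naming a part, follows its definition of symptomatic deterioration with: "Every effort should be made to document the objective progression even after discontinuation of treatment".

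In Cohort Expansion the last planned CT is at the EOT Visit (Table 5, footnote 12), held promptly once withdrawal is decided (8.1.1.5). After that comes one visit 30 days after the last dose, restricted to SAEs (8.1.1.6, 9.2.5).

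The endpoints are not restricted to time on treatment. Section 12.5.3.3 states: "Progression-free survival is defined as the number of days from Day 1 in Cycle 1 to first PD or death". Section 12.5.3.4 defines DoR as "the number of days from the first documentation of objective tumor response (CR or PR) to the date of first PD or death". For both, 12.3 says that "the quartile estimates of PFS and DoR from the Kaplan-Meier product limit algorithm will be presented", with 95% confidence intervals and no formal tests.

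**The concern.** The events that PFS and DoR count can occur after treatment has ended, but in Cohort Expansion no scheduled visit would find them. Section 8.3.4.1 lists many reasons to stop treatment other than progression, several of them ocular, and severe ocular toxicity is what led to Amendment 4. A patient who stops for such a reason, or for symptomatic deterioration, can only be censored at about the time of stopping.

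Two things are at stake. Events are lost from a small data set: 20 to 30 patients in two or three indication arms, which 12.9 expects to yield preliminary efficacy data. And Kaplan-Meier treats a censored patient as having the same outlook as those still at risk. If patients who stop have a different outlook, the estimate no longer describes PFS as 12.5.3.3 defines it. A statistical analysis plan can set the censoring rule, but it cannot recover dates that were never collected.

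**Working it through.** **Figures in the protocol.** Nine q3wk cycles: 9 × 3 = 27 weeks, as stated in 8.1. Nine 3q4wk cycles: 9 × 4 = 36 weeks, as stated. Dose Escalation follow-up: 4 × 6 = 24 weeks, as stated. The protocol gives no assumed PFS, stop rate or censoring rate, so every figure below is an illustration on assumed inputs.

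**What happens to each type of patient in Cohort Expansion.**

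1. Stops for PD: has an event; unaffected.
2. Completes nine cycles without PD: observation ends at about 27 weeks (36 on the old schedule), with continued treatment under a separate extension protocol (8.1). This is administrative censoring and not informative in itself.
3. Stops for toxicity or symptomatic deterioration without PD: one EOT scan, then censored. Death within 30 days of the last dose is still captured as an SAE (8.1.1.6). Later progression or death has no planned route into the database.
4. Stops for toxicity but stays in the trial: 8.1.1.5 triggers the EOT Visit on PD, new therapy or withdrawal from the trial, and 8.3.4.2 does not list toxicity as a reason to leave the trial. The text sends this patient to follow-up visits (8.3.4.3) that do not exist (8.1.1.4).

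**Illustration A: the hazard changes after stopping.** Let progression on treatment have hazard λ and stopping without PD have independent hazard μ. A share p stops before PD, so μ/λ = p/(1 − p). After stopping, the hazard is HR × λ. With x = λt, m = μ/λ and k = 1 + m, PFS including post-treatment events is

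S(x) = exp(−kx) + m × [exp(−kx) − exp(−HR·x)] / (HR − k).

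Kaplan-Meier with censoring at the stop returns the on-treatment median, x = ln 2 = 0.6931. Solving S(x) = 0.5:

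| p | HR | m | x at S = 0.5 | 0.6931/x − 1 |
|---|---|---|---|---|
| 0.2 | 1.0 | 0.250 | 0.6931 | 0% |
| 0.2 | 1.5 | 0.250 | 0.6691 | 3.6% |
| 0.2 | 3.0 | 0.250 | 0.6273 | 10.5% |
| 0.3 | 1.5 | 0.429 | 0.6548 | 5.9% |
| 0.3 | 3.0 | 0.429 | 0.5922 | 17.0% |

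For an on-treatment median of 3 months, the last row means 3.0 reported against 3 × 0.5922/0.6931 = 2.56 months. Simulation gave the same 2.56. An HR below 1 would reverse the sign.

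**Illustration B: time to stopping correlated with time to progression.** Simulated with 200,000 patients per scenario: exponential PFS with true median 18 weeks, Gaussian-copula correlation rho, and observation ending at the stop or at week 27.

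| Share stopping without PD | Median, rho 0 | rho 0.5 | rho 0.8 |
|---|---|---|---|
| 10% | 18.1 | 19.2 | 20.2 |
| 20% | 17.9 | 20.3 | 22.4 |
| 30% | 18.0 | 21.6 | 25.3 |

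Adding 24 weeks of progression follow-up brought the median back to about 18 weeks in every scenario.

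**Events lost.** With no early stops, 30 patients with an 18-week median would yield 30 × (1 − 0.5^(27/18)) = 30 × 0.646 = 19.4 events by week 27. The scenarios above yield 12.5 to 18.0, so 1.4 to 6.9 events per 30 patients are lost to stops without PD. Even at rho 0 the loss is 1.4, 2.7 and 4.1 events at 10%, 20% and 30% stops (18.0, 16.7 and 15.3 observed), so it does not depend on the censoring being informative.

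**The case against.** The strongest objection is that Illustration A shows no failure of Kaplan-Meier. Stopping there is independent of on-treatment progression, and the estimator returns the on-treatment median correctly. The 3.6% to 17% is the gap between on-treatment PFS and PFS as defined. That is right, and the figure should be read that way. Illustration B does violate the Kaplan-Meier assumption, but only because a correlation was assumed. A reader might infer that PFS and DoR are shown to be informatively censored and overstated. The documents do not support that: nothing in them says that patients who stop for toxicity progress sooner. It is more plausible for symptomatic deterioration, which is where the instruction in 12.5.3.1 sits.

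Other stronger readings also fail.

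- That nothing is recorded after treatment: there is an EOT CT, optional unscheduled CTs (Table 5), and capture of deaths within 30 days, including deaths from progression (11.1.3).
- That the 27-week limit is part of the bias: it is administrative.
- That the two parts become non-comparable: no comparison is planned, and 12.3 presents them separately.

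Precision is a fair point too. Arms hold about 20/3 ≈ 7 to 30/2 = 15 patients. With a 3-month median and 25% stops, the central 95% range of a simulated Kaplan-Meier median is about 1.3 to 6.4 months for 15 patients and 1.6 to 5.2 for 30. A shift of 0.1 to 0.4 months is well inside that, and 12.3 already warns that few events may limit the method. This lowers the importance of the point, but lost events make the imprecision worse.

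Finally, the effort asked for in 12.5.3.1 is not a visit schedule, and 8.3.4.3 could be read as general text overridden by 8.1.1.4. But neither section says so, and a site has no way to tell which governs.

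**Conclusion.** The inconsistency stands. In Cohort Expansion no tumour assessment is scheduled after the EOT Visit, while 8.3.4.3 and 12.5.3.1 ask for follow-up and documented progression without exempting that part. Patients who stop without PD for toxicity or symptomatic deterioration are censored at about treatment stop, against endpoint definitions that run to PD or death.

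The loss of events follows from the design. Informative censoring is plausible but not demonstrated, and neither its size nor its direction can be derived from the protocol. The range of no bias up to about 17% on the median rests wholly on assumed stop rates of 20-30%, post-stop hazard ratios of 1 to 3 and exponential times; the correlated model shows that larger shifts are possible under stronger assumptions.

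The affected endpoints are secondary and descriptive, and the primary safety endpoint is untouched. The point is worth acting on because the repair is cheap and the data cannot be recovered later.

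**What to change.** 1. Reconcile 8.1.1.4, 8.3.4.3 and 12.5.3.1, so that each states which part it applies to.
2. For Cohort Expansion patients who stop without PD, record the date and source of progression, start of new anti-cancer therapy, and death, as found in routine care. Collect these up to the end of trial as defined in 8.2, not beyond it: open-ended collection to a database cut-off would conflict with that rule. Add no scans or visits.
3. Add one PFS and DoR sensitivity analysis that counts discontinuation for toxicity, symptomatic deterioration or new therapy as an event, and report the number censored by reason. These details can sit in the statistical analysis plan, which 12.1 already says will be updated for Amendment 4.
4. If no post-treatment data are to be collected, limit 8.3.4.3 and 12.5.3.1 to Dose Escalation and label Cohort Expansion PFS and DoR as on-treatment estimates.

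Cost: a short eCRF page, a small effort at sites and one extra analysis. Some progression dates will not rest on scheduled RECIST scans; these should be flagged in the data and the listings.

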8.1.1.5 End of Trial Visit (EOT)

Dose Escalation Part

If a patient completes all follow-up visits, the EOT Visit should be performed four weeks after the end of the Follow-up Visit 4 period.

In case of withdrawal from the trial, the EOT Visit will be performed as soon as possible. The EOT Visit will include most assessments performed at the Screening Visit, and response assessments.

Cohort Expansion Part

If the patient shows PD, is to start new anti-cancer treatment or withdraws from trial due to another reason during treatment, the EOT Visit should be performed as soon as possible after decision of withdrawal.

The EOT Visit will include most assessments performed at the Screening Visit, and response assessments.

8.1.1.6 Safety Follow-up Visit

Dose Escalation Part

Patients who withdraw from the trial before Follow-up Visit 1 will return for a Safety Follow-up Visit 30 days after the last dose of IMP. In the Safety Follow-up Visit, only SAEs will be

Final 5.0 (incorporating Protocol Amendment 4) 06 Jul 2017

assessed. If the patient has died within the 30 days this should be entered as an AE in the eCRF and reported as an SAE.

Cohort Expansion Part

Patients who withdraw from the trial will return for a Safety Follow-up Visit 30 days after the last dose of IMP. In the Safety Follow-up Visit, only SAEs will be assessed. If the patient has died within the 30 days this should be entered as an AE in the eCRF and reported as an SAE.

8.2 Trial Duration and End of Trial

The enrollment period is planned to last approximately 21 months.

The trial will be stopped when the last patient enrolled in the Cohort Expansion part completes the trial or when the last ongoing patient has discontinued treatment and attended the Safety Follow-up Visit, whichever occurs first.

The end of trial ("trial completion") is defined as the date of the last protocol-specified visit/assessment for the last patient in the trial or the date the trial is closed by the sponsor, whichever occurs first.

All materials or supplies provided by the sponsor will be returned to the sponsor or designee upon trial completion, as directed by the site monitor. The IEC/IRB will be notified when the trial has been completed.

Genmab A/S reserves the right to temporarily suspend or prematurely discontinue this trial either at a single site, multiple sites or at all sites at any time for reasons including, but not limited to, safety or ethical issues, inaccurate or incomplete data recording, noncompliance, or unsatisfactory enrollment with respect to quality or quantity.

If the trial is prematurely terminated or suspended, Genmab A/S (or its representative) will inform the investigators/institutions and the regulatory authority(ies) of the termination or suspension and the reason(s) for the termination or suspension, in accordance with applicable regulatory requirement(s). The IEC/IRB should also be informed and provided with reason(s) for the termination or suspension by the sponsor or by the investigator/institution, as specified by the applicable regulatory requirement(s). In addition, arrangements will be made for the return of all unused trial drug and other materials or supplies provided by the sponsor.

8.2.1 Trial Stopping Criteria

If any of the following occur, administration of the trial drug will be stopped and no additional patients will be enrolled into the trial:

- 1) Grade ≥ 3 anaphylactic reaction to tisotumab vedotin (HuMax-TF-ADC) in any patient.
- 2) Other events not including DLT that, in the judgment of the sponsor Medical Officer, are deemed serious enough to warrant immediate review and potential stop of other dosing by the DMC.
- 3) Any other safety finding assessed as related to tisotumab vedotin (HuMax-TF-ADC) that, in the opinion of the sponsor, contraindicates further dosing of trial patients.

Final 5.0 (incorporating Protocol Amendment 4)

If any of the above-listed events occur, a prompt cumulative review of safety data and the circumstances of the event in question will be conducted by the DMC to recommend whether dosing and trial entry should be resumed, whether the protocol will be modified, or whether the trial will be discontinued permanently. Review and approval by the sponsor's Safety Committee is required for resumption of the trial in the event that the trial is interrupted because of one of the above-listed events. Where applicable, regulatory authorities IECs/IRBs will be notified of any actions taken with the trial.

Any patients who have already received the trial drug and are currently in the trial at the time trial stopping criteria are met will continue to be monitored by the investigator for safety.

Withdrawal criteria for individual patients are provided in Section 8.3.4.

8.3 Trial Population

The patient population in the Dose Escalation part will encompass patients with advanced (locally advanced and/or metastatic) cancer of the ovary, cervix, endometrium, bladder, prostate (CRPC), esophagus or lung (NSCLC) who have failed available standard treatments or who are not candidates for standard therapy.

The specific indications for the Cohort Expansion part will be decided once the RP2D has been determined. The inclusion and exclusion criteria for a reduced number of previous lines of treatment will be specified for all potential indications.

The Dose Escalation part of the trial is planned to be performed in a maximum of three sites in Denmark, UK and the USA. The Cohort Expansion part of the trial is planned to be performed in the ongoing countries and in Hungary and Belgium.

Thirty two to 44 patients are planned to be enrolled in the trial. Assuming an anticipated screen failure rate of 30%, 57 to 76 patients will be screened in total.

- In the Dose Escalation part: 12 to 24 patients are planned to be enrolled: three to six patients per dose level for three dose levels (plus a potential intermediate dose cohort).
- In the Cohort Expansion part: 20 to 30 patients are planned to be enrolled in two or three indication arms.

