The Dose Escalation part is a standard 3 (+3) design. In each dose cohort, the initial three patients must include at least two different cancer types. A maximum of three dose levels is anticipated. Patients may receive up to 12 cycles of treatment.

The Cohort Expansion part will have a parallel group design, with a minimum of 20 and a maximum of 30 patients in two or three indication arms. Patients in the Cohort Expansion part will be treated with the RP2D from the Dose Escalation part. Patients may receive up to nine cycles of treatment.

A Data Monitoring Committee (DMC) will evaluate safety data during the Dose Escalation part of the trial and will convene in the event of safety signals in the Cohort Expansion part of the trial.

Severe ocular toxicity has been observed at 1.2 mg/kg 3q4wk (the RP2D for the Cohort Expansion part), and an urgent safety Protocol Amendment 4.0 has been implemented. Patients will not further receive the dosing schedule 3q4wk; instead tisotumab vedotin 2.0 mg/kg will be administered once every three weeks (q3wk).

TRIAL POPULATION AND MAIN CRITERIA FOR INCLUSION/EXCLUSION:

The patient population in the Dose Escalation part will encompass patients with advanced (locally advanced and/or metastatic) cancer of the ovary, cervix, endometrium, bladder, prostate (castration-resistant prostate cancer [CRPC]), esophagus or lung (non-small cell lung cancer [NSCLC]) who have failed available standard

Final 5.0 (incorporating Protocol Amendment 4) 06 Jul 2017

treatments or who are not candidates for standard therapy. The specific indications for the Cohort Expansion part will be decided once the RP2D has been determined from the Dose Escalation part.

Patients cannot be enrolled before all inclusion criteria (including test results) are confirmed.

Inclusion Criteria:

- For the Dose Escalation part: Patients with relapsed, advanced and/or metastatic cancer of the ovary, cervix, endometrium, bladder, prostate, esophagus, or NSCLC who have failed available standard treatments or who are not candidates for standard therapy.
- For the Cohort Expansion part: The specific indications for the Cohort Expansion part will be decided once the RP2D has been determined. After implementation of the urgent safety measure (Protocol Amendment 4), no patients will further receive the 3q4wk schedule; instead, tisotumab vedotin (HuMax-TF-ADC) 2.0 mg/kg will be administered once q3wk.

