- Other: ongoing, significant, uncontrolled medical condition; presence of CTCAE (Common Terminology Criteria for Adverse Events) grade ≥ 2 peripheral neuropathy; clinically significant active viral, bacterial or fungal infection requiring intravenous treatment with antimicrobial therapy starting less than four weeks prior to first dose or oral treatment with antimicrobial therapy starting less than 10 days prior to first dose; known human immunodeficiency virus seropositivity; positive serology (unless due to vaccination or passive immunization due to Ig therapy) for hepatitis B defined by positive test for hepatitis B surface antigen (HBsAg) and/or positive test for antibodies to hepatitis B surface and core antigens (anti-HBs and anti-HBc); positive serology for hepatitis C based on test at screening; inflammatory bowel disease including Crohn's disease and colitis ulcerosa; inflammatory lung disease including moderate and severe asthma and chronic obstructive pulmonary disease (COPD) requiring chronic medical therapy; ongoing acute or chronic inflammatory skin disease.
- Ophthalmological: active ocular surface disease at baseline (based on ophthalmological evaluation); history of cicatricial conjunctivitis (as evaluated by an ophthalmologist).

NUMBER OF PATIENTS: Approximately 46 to 63 patients will be screened to ensure that 32 to 44 patients (anticipated screen failure rate of 30%) complete the trial.

In the Dose Escalation part: 12 to 24 patients are planned to be enrolled: three to six patients per dose level for three dose levels (plus a potential intermediate dose cohort).

In the Cohort Expansion part: 20 to 30 patients are planned to be enrolled in two or three indication arms.

TRIAL TREATMENT(S): Tisotumab vedotin (HuMax-TF-ADC) will be administered as an intravenous infusion over a minimum of 30 minutes on Days 1, 8 and 15 of each cycle (one treatment cycle is 28 days). Each patient's dose will be calculated based on the patient's weight rounded to the nearest kilogram. Preventive eye therapy should be administered in relation to infusions.

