12.9 Sample Size Estimation

A maximum of 24 patients are planned to be enrolled in the Dose Escalation part of the trial. As the primary objective of the trial is to establish the tolerability of tisotumab vedotin (HuMax-TF-ADC), the sample size is based only on the 3 (+3) dose escalation MTD design and the expected maximum of three dose levels (plus a potential intermediate dose cohort). The classical 3 (+3) dose escalation MTD design aims to determine MTD with the fewest possible patients exposed. Taking into account an anticipated screen failure rate of 30%, 18 to 35 patients will be screened.

In the Cohort Expansion part, up to 20-30 patients in two or three indication arms are expected to provide more information on the safety of the compound at the RP2D level as well as preliminary efficacy data for the more frequent dosing regimen.

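### The planned total of 32–44 patients does not equal the sum of its two parts (32–54), and the 57–76 screened in Section 8.3 does not follow from 32–44 at 30% screen failure and conflicts with the synopsis (46–63)

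*Protocol*

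**What the plan says.** Protocol Section 8.3 (Trial Population) gives an overall size, "Thirty two to 44 patients are planned to be enrolled in the trial", and a screening number, "Assuming an anticipated screen failure rate of 30%, 57 to 76 patients will be screened in total". Two bullets follow:

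- "In the Dose Escalation part: 12 to 24 patients are planned to be enrolled"
- "In the Cohort Expansion part: 20 to 30 patients are planned to be enrolled in two or three indication arms"

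The synopsis, under Number of Patients, lists the same two part sizes but says: "Approximately 46 to 63 patients will be screened to ensure that 32 to 44 patients (anticipated screen failure rate of 30%) complete the trial".

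The part sizes are repeated elsewhere. The synopsis design paragraph describes the Cohort Expansion "with a minimum of 20 and a maximum of 30 patients in two or three indication arms", and Sections 8.1.1.2 and 9.2.2 also give 20 to 30. Section 12.9 says "A maximum of 24 patients are planned to be enrolled in the Dose Escalation part of the trial" and, for that part alone, "Taking into account an anticipated screen failure rate of 30%, 18 to 35 patients will be screened". Section 12.9 gives no total for the whole trial.

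**The concern.** There are two separate inconsistencies.

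1. **The total against its parts.** The lower ends add up, but the upper ends do not. A reader cannot tell whether up to 44 or up to 54 patients are planned. A 45th patient could fall within both part limits and still exceed the stated total.
2. **The screening number.** Section 8.3 and the synopsis start from the same 32–44 patients and the same 30% failure rate, yet arrive at different numbers screened.

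A smaller wording point goes with these. The synopsis says the 32–44 patients will complete the trial, while Section 8.3 says they are enrolled. Section 12.3 defines completion as having had all planned visits. An allowance for screen failure covers entry only and makes no provision for later withdrawal, so it can support an enrolled number but not a completing one.

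Ethics committees, regulators and sites rely on the planned size and the screening load, so the protocol should give one answer for each.

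**Working it through.** **Inputs**

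- Dose Escalation: 12–24 (Section 8.3, synopsis; maximum of 24 repeated in Section 12.9).
- Cohort Expansion: 20–30 (Section 8.3, synopsis, Sections 8.1.1.2, 9.2.2 and 12.9).
- Screen-failure rate: 30% (Section 8.3, synopsis, Section 12.9).

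**Step 1: the protocol's screening convention.** Screened = enrolled / (1 − 0.30), rounded up.

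- Section 12.9: 12/0.70 = 17.14 → 18; 24/0.70 = 34.29 → 35. This reproduces the stated 18–35.
- Synopsis: 32/0.70 = 45.71 → 46; 44/0.70 = 62.86 → 63. This reproduces the stated 46–63.

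**Step 2: the total from its parts.**

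- Minimum: 12 + 20 = 32, as stated.
- Maximum: 24 + 30 = 54, against 44 stated. The difference is 10, and 10/44 = 22.7%.
- 44 equals 24 + 20, the Dose Escalation maximum plus the Cohort Expansion minimum. Whether it arose that way is conjecture.

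**Step 3: the 57–76 in Section 8.3.**

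| Enrolled | Screened at 30% failure | Stated in 8.3 |
|---|---|---|
| 32–44 (stated total) | 46–63 | 57–76 |
| 32–54 (sum of parts; 54/0.70 = 77.14 → 78) | 46–78 | 57–76 |

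Multiplying by 1.30 instead does not help: 32 × 1.30 = 41.6 → 42 and 44 × 1.30 = 57.2 → 58.

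Working backwards:

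- 57 × 0.70 = 39.9 and 76 × 0.70 = 53.2, so 57–76 screened would yield about 40–53 enrolled.
- For 32–44 enrolled, the implied failure rate is 1 − 32/57 = 43.9% at the lower end and 1 − 44/76 = 42.1% at the upper end.
- With 54 enrolled, 1 − 54/76 = 28.9%. The upper figure of 76 is therefore close to what 54 would need, but the lower figure of 57 fits neither total.

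**The case against.** The strongest reply is that this is clerical. The limits that govern enrolment are those of the two parts, and they are consistent throughout. Section 12.9 bases the sample size on the 3 (+3) design and states no total. Section 12.3 rules out formal tests. By version 5.0 the dose for the expansion had already been chosen, so the Dose Escalation range is largely historical. All of this stands, and it limits the consequence. It does not remove either contradiction.

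Four further points:

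- **44 may be a deliberate cap.** This is possible, but no section says so. A cap would also tie the two parts together: with 24 in Dose Escalation, only 44 − 24 = 20 could enter the expansion, and a full expansion of 30 would leave 44 − 30 = 14 for Dose Escalation. The documents show that the figures disagree, not which one was intended.
- **Replacements.** Section 8.3.4.5 has patients who leave in Cycle 1 for reasons other than a DLT replaced, a provision that ends with Amendment 4. Actual enrolment could therefore exceed planned part sizes. This can only raise the total, and Section 8.3 attributes 57–76 to screen failure alone.
- **The minimum of 12.** Three dose levels at three to six patients give 9–18, and four cohorts give 12–24. The lower figure therefore seems to count the intermediate cohort, which is only potential, or to assume six patients at one level. The total of 32 is thus confirmed only as the sum 12 + 20, and 18–35 only as 12–24 divided by 0.70.
- **Completing versus enrolled.** The lines that follow in the synopsis speak of enrolment, so the intended meaning can be inferred. This is a wording correction and adds little weight.

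**Conclusion.** The point holds. The stated maximum of 44 is 10 below the sum of the stated part maxima, 54. The 57–76 screened in Section 8.3 fits neither 32–44 (46–63) nor 32–54 (46–78) at 30% failure, and it contradicts the synopsis. If the part sizes stand, the screening maximum is 78, against 63 in the synopsis and 76 in Section 8.3. The synopsis range of 46–63 is sound arithmetic for 32–44 and is in doubt only through the upper total it inherits.

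This rests on the part sizes being as stated, on the 30% rate, on rounding up as Section 12.9 does, and on planned numbers that exclude replacements. The consequence is limited to the planned size and screening figures. No test, power, error rate or stated precision is touched. It should be corrected because the planned size is a basic figure of the protocol.

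**What to change.** Choose one total and state it identically in the synopsis and Section 8.3:

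- **If the part sizes stand:** 32–54 enrolled and 46–78 screened, noting that these are planned numbers before any replacements.
- **If 44 is a real overall cap:** say so, give 46–63 screened in both places, and state that the Cohort Expansion maximum falls as Dose Escalation enrolment rises.

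In either case, change the synopsis so that the screening allowance refers to patients enrolled and not to patients completing the trial. The 18–35 in Section 12.9 can stay.

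The cost is a correction of a few figures and one verb in two places. Keeping the part sizes changes neither design nor analysis. Declaring a cap would also need the sentence on how it limits the expansion.
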